### **Recruitment/Setting**

The all participants of this study have been selected after complete clinical examination has been done with full medical and dental history , history of medications and history of hospitalization. In patients who receive dental treatment as an usual care in clinics of Pediatric Dentistry and Dental Public Health Department at faculty of dentistry, Ain-Shams University.

Informed consent designed to include all data about dental procedures in this study and clear more details about time consuming in the procedure and follow up visits, used materials and adverse event of this procedure . All participants have the right to withdraw from this study at any time .The consent will be assigned from each patient by the patient's parents or guardians after explanation of the study.

The full mouth rehabilitation will be performed by postgraduate student registered at the master Degree at the Pediatric Dentistry and Dental Public Health Department Faculty of Dentistry, Ain- Shams University

All subjects receive instructions on oral health, particularly in relation to oral hygiene and sugar consumption.

### **Material**

|                |                                       |                              |
|----------------|---------------------------------------|------------------------------|
| Material name: | ACTIVA BIOACTIVE restorative material | Fuji IX                      |
| Manufacture:   | PULPDENT                              | GC America                   |
| Material type: | Enhanced resin modified glass ionomer | High-viscosity glass ionomer |

## **Sample Grouping**

The 60 participant will be randomly divided into two group according to used material as follow:

**Group I (control):** will consist of 30 teeth that will be restored with conventional Atraumatic restorative treatment (ART) using by high-viscosity glass ionomer (Fuji IX)

**Group II:** will consist of 30 teeth that will be restored with Atraumatic Restorative Treatment (ART) using ACTIVA BIO ACTIVE restorative material

### **Steps of Procedure in group (control):**

Atraumatic Restorative Treatment (ART) performed according to Frencken et al. guidelines (28)

- Maintain relative isolation of the operatory field with cotton rolls.
- Remove caries: using only hand excavators compatible with the size of the carious cavity. Both infected and affected dentin should be removed from the dentin–enamel junction. the affected dentin will be maintained in the remaining walls. Thin, unsupported enamel was carefully removed using a hatchet placed on the enamel with slight pressure.
- Clean the cavity: cavity walls should be cleaned with cotton balls moistened with water
- Condition the dentin: apply a drop of 11.5% polyacrylic acid on a cotton ball for 15 s.
- Then, wash the cavity with three cotton balls moistened with water and dry using three more cotton balls.
- encapsulated GIC(Fuji IX), the plunger was placed on a hard surface and a mechanical mixer was used to mix the capsules for 10 seconds. The capsule was then placed into the applicator to insert the GIC into the cavity.
- After inserting the GIC, a gloved finger coated with petroleum jelly was used to apply pressure to the GIC for 1 minute.
- Occlusion was checked and excess material was removed with a carver. Restorations were coated with a layer of petroleum jelly to prevent sorption during occlusal checking.
- petroleum jelly was removed from the surface using at least two cotton wool pellets. GC Coat was applied to the surfaces of final restorations and light-cured for 20 seconds
- Instruct the patient not to eat solid food for 1 hour.

**Steps of Procedure in group :**

- Maintain relative isolation of the operatory field with cotton rolls.
- Remove caries: using only hand excavators compatible with the size of the carious cavity. Both infected and affected dentin should be removed from the dentin–enamel junction. the affected dentin will be maintained in the remaining walls. Thin, unsupported enamel was carefully removed using a hatchet placed on the enamel with slight pressure.
- Clean the cavity: cavity walls should be cleaned with cotton balls moistened with water and dry using three more cotton balls.
- Insert a ACTIVA BIOACTIVE restorative material to the cavity without application of acid etching or bond
- Occlusion was checked and excess material was removed with a carver.
- Instruct the patient not to eat solid food for 1 hour.

## Study procedure

### In VIVO Study

Atraumatic Restorative Treatment will be formed by two different restorative materials (ACTIVA BIOACTIVE and High- viscosity Glass ionomer) and long term survival of restorative material will be evaluated at 3,6 and 9 months .

### Outcomes

**The outcome of this study** is the longevity of ACTIVA BIOACTIVE restorative material versus high –viscosity glass ionomer in (ART) in Class I carious cavity of primary teeth

### Longevity of the restoration

Treatment longevity will be evaluated clinically after 3, 6 and 9 months according to the Frencken and Holmgren criteria (29) in the class I restorations using sharp sickle shaped explorers, WHO CPI periodontal probes, which has a ball tip with 0.5 mm diameter,plane mirrors, and light source of dental unit.

The codes and criteria used to evaluate the ART restorations are found in the Table

| Score | Criteria(17)  |
|-------|---|
| 0     | Present, good  |
| 1     | Present, slight marginal defect for whatever reason, at any one place which is less than 0.5 mm in depth.

No repair is needed.     |
| 2     | Present, marginal defect for whatever reason, at any one place which is deeper than 0.5 mm but less than 1.0 mm.

Repair is needed. |
| 3     | Present, gross defect of more than 1.0 mm in depth.

Repair is needed.  |
| 4     | Not present, restoration has (almost) completely disappeared.

Treatment is needed.   |
| 5     | Not present, other restorative treatment has been performed.   |

|   |  |
|---|--|
| 6 | Not present, tooth has been extracted.  |
| 7 | Present wear and tear gradually over larger parts of the restoration but is less than 0.5 mm at the deepest point.

No repair is needed. |
| 8 | Present, wear and tear gradually over larger parts of the restoration which is deeper than 0.5 mm

Repair is needed.                     |
| 9 | Unable to diagnose  |

**Note :** Restorations considered to have survived are scored by codes: 0,1,7; those considered to have failed by codes: 2,3,4,8; while those that are considered to be unrelated to success and failure are codes:5,6

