## **Adverse Event Reporting**

### **Adverse events in vivo part of study :**

- 1-partial or complete failure of restoration that will need to be repaired
- 2-recurrent caries around restorations
- 3-Inflammatory reactions of pulps of restored teeth that will need pulp therapy
- 4-Infection of pulp of restored teeth that may develop an abscess or facial cellulitis which will need pulp therapy or extraction with or without space maintainer.
- 5-time consuming during dental procedure and follow up visits

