### **Statistical analysis**

Data will be collected, tabulated, and statistically analyzed using suitable statistical test to achieve the aim of this study .

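### The longevity score sets aside every re-treated or extracted tooth whatever the cause, so failures of the study restoration can drop out of the clinical outcome

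*Combined protocol and SAP*

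**What the plan says.** Longevity of the restoration is the stated clinical outcome (Outcomes). It is scored on a ten-code scale, and the In VIVO Study section fixes the visits: "long term survival of restorative material will be evaluated at 3,6 and 9 months".

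The note under the scoring table treats codes 0, 1 and 7 as survival and codes 2, 3, 4 and 8 as failure. Code 5 is "Not present, other restorative treatment has been performed" and code 6 is "Not present, tooth has been extracted". Both are put outside the outcome: "while those that are considered to be unrelated to success and failure are codes:5,6". The table and note ask for no reason for either code. They also do not say what happens at later visits to a tooth already scored as failed.

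The adverse event section for the in vivo part lists "partial or complete failure of restoration that will need to be repaired", "recurrent caries around restorations", and pulp infection "which will need pulp therapy or extraction with or without space maintainer". It does not refer to the longevity codes.

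The Statistical analysis section says only that data will be "statistically analyzed using suitable statistical test to achieve the aim of this study".

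**The concern.** Codes 5 and 6 describe what was done to the tooth, not why. Some re-treatments and extractions will have nothing to do with the study restoration. Others will be its direct consequence, and the adverse event list names the routes. Calling all of them unrelated to failure removes some real failures from the outcome the trial is meant to measure.

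There are two ways for a failure to be lost:

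- **Between visits.** The restoration fails and the tooth is replaced or extracted before anyone scores it. The next visit records code 5 or 6.
- **After a scored failure.** The table itself says that repair or treatment is needed for codes 2, 3, 4 and 8. A tooth scored 3 at three months and then re-treated may be code 5 at nine months. With no carry-forward rule, a table of nine-month scores would not show it as failed.

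Each loss can only raise apparent survival in its arm. If the share lost differs by material, the comparison between arms is distorted. With 30 teeth per arm, a few teeth are enough to matter.

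**Working it through.** **Text check.** Set the note beside the adverse event list. A tooth extracted because infection developed under the study restoration is an anticipated adverse event in one section and unrelated to failure in the other. No section links the two records, and the Statistical analysis section has no rule that would reclassify the tooth. Codes 5 and 6 might be excluded, censored or left in the denominator. Under none of these are they failures.

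**Inputs.** From the plan: 30 teeth per arm (Sample Grouping). It gives no failure rate and no frequency for codes 5 and 6, so there is no plan figure to reproduce. The sample-size formula uses 0.07 but labels it a p-value; here 7% serves only as a convenient low failure rate. All failure rates and masking shares below are assumptions.

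**(a) One arm, 3 scored failures and k teeth coded 5 or 6.** Failure is 3/(30 − k) if they are excluded, and (3 + k)/30 if all were true failures.

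| k | Excluded | All failures |
|---|---|---|
| 1 | 3/29 = 10.3% | 4/30 = 13.3% |
| 2 | 3/28 = 10.7% | 5/30 = 16.7% |
| 3 | 3/27 = 11.1% | 6/30 = 20.0% |

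**(b) Equal masking in both arms.** Let c be the true failure rate and s the share of failures that end as code 5 or 6 and are excluded. Each tooth is a seen failure with probability c(1 − s), masked with probability cs, or a survivor with probability 1 − c. Exact enumeration at 30 per arm, uncorrected chi-square test, two-sided 5%, gives this power:

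| Share masked | 7% vs 40% | 7% vs 20% |
|---|---|---|
| 0% | 89.4% | 32.8% |
| 5% | 88.3% | 31.6% |
| 10% | 87.0% | 30.2% |
| 25% | 81.5% | 25.4% |
| 50% | 66.8% | 15.8% |
| 75% | 39.0% | 5.0% |

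At 10% masked the loss is 89.4 − 87.0 = 2.4 points, or 32.8 − 30.2 = 2.6 points.

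**(c) Masking in one arm only, true failure 20% in both.** The apparent rate in the masked arm is (1 − s)c/(1 − sc).

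| Share masked | Apparent rate | False difference | Rejection rate of the 5% test |
|---|---|---|---|
| 0% | 20.0% | 0 | 4.9% |
| 10% | 0.18/0.98 = 18.4% | 1.6 points | 5.4% |
| 25% | 0.15/0.95 = 15.8% | 4.2 points | 7.2% |
| 50% | 0.10/0.90 = 11.1% | 8.9 points | 14.8% |

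**(d) A real difference hidden.** With 9 failures of 30 against 2 of 30, Fisher's exact test gives p = 0.042. If 3 of the 9 are coded 5 or 6 and excluded, the counts are 6/27 against 2/30 and p = 0.13.

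**The case against.** Four arguments carry weight.

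- **The coding is taken from a cited, published set of criteria.** That source cannot be seen here, so it cannot be said whether it has its own rule on cause. This supports keeping the published coding in the report. It does not make a replacement caused by failure unrelated to failure.
- **The size is not shown from the plan.** Every rate above is assumed, and at 10% masking or less the effect is small. With 7% against 20%, power is only 33% with no masking at all, so sample size is the larger limit in that scenario. This stands.
- **Exclusion or censoring is an inference.** The plan names no analysis, so part of the difficulty comes from the missing analysis plan. But the classification itself is written down, and no choice of test turns a code 5 or 6 into a failure.
- **Re-classification can err the other way.** Participants receive full mouth rehabilitation, so re-treatment for other reasons is possible. Counting codes with no known reason as failures in the primary analysis would be hard to defend.

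Two stronger readings are tempting. A reader might infer that these failures vanish from the trial altogether. They need not: they may still be recorded as adverse events, and the gap is that nothing carries them into the longevity score. A reader might also infer that the rule favours one material. The documents give no frequency by arm, so they support no direction.

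**Conclusion.** The point holds for the longevity outcome. The note classes every code 5 and 6 as unrelated to failure whatever the cause, while the same protocol foresees causes that are failures of the study restoration or complications in the restored tooth. Failures treated between visits are not counted. Failures scored at a visit are not safely counted either, because nothing says that they stay failures after re-treatment.

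The reading of the text is firm; the impact is not. It rests on an unknown number of code 5 and 6 teeth that followed failure, and on how that number splits between arms. The assumed scenarios run from negligible (10% of failures masked or less) to material (50% masked in one arm only). The plan should be changed, since the reason for a code 5 or 6 may not be recoverable if it is not recorded at follow-up, and a rule chosen after the results are seen invites bias.

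**What to change.** Amend the note under the scoring table. The change concerns classification for analysis only and leaves care of the child as it is.

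1. Record the reason for every code 5 and 6.
2. State that the first code 2, 3, 4 or 8 is a failure and remains one at all later visits.
3. In the primary analysis, count a code 5 or 6 as failure when the recorded reason is loss or defect of the study restoration, recurrent caries around it, or pulp pathology of the restored tooth. Censor at the last scored visit when the reason is documented as unrelated, including natural tooth loss, or is unknown.
4. Report codes 5 and 6 by arm and reason. Add one sensitivity analysis that counts all of them as failures, and keep the cited published coding as a secondary table.

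The cost is one extra field in the follow-up record and a few sentences. The primary result becomes slightly less directly comparable with reports that use the published coding, which the secondary table largely offsets.

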## **Data Management:**

All data will be entered electronically.

Participant's data will be stored in numerical order in secure place and limited access files. Soft copies of the files will be protected by password access.

The hard copy will be kept confidential and private with the investigator throughout the study.

## **Adverse Event Reporting**

### **Adverse events in vivo part of study :**

- 1-partial or complete failure of restoration that will need to be repaired
- 2-recurrent caries around restorations
- 3-Inflammatory reactions of pulps of restored teeth that will need pulp therapy
- 4-Infection of pulp of restored teeth that may develop an abscess or facial cellulitis which will need pulp therapy or extraction with or without space maintainer.
- 5-time consuming during dental procedure and follow up visits

### **Adverse events in vitro part of study**

There is no adverse events in this part.

### **Statistical analysis**

Data will be collected, tabulated, and statistically analyzed using suitable statistical test to achieve the aim of this study .

